3.4 AIMS, OBJECTIVES AND ENDPOINTS

The trial aims to determine the clinical and cost effectiveness of NAVA technology (NAVA monitoring and NAVA mode) compared to conventional IMV in patients with risk factors for difficult or prolonged weaning from invasive mechanical ventilation.

We have included as our trial outcomes, the core outcome set for trials of interventions intended to modify IMV duration developed by members of our group [3].

3.4.1 PRIMARY OBJECTIVE AND OUTCOME

Our primary objective is to determine the effectiveness of NAVA technology for reducing the duration of mechanical ventilation compared to conventional IMV.

Our primary outcome is duration of mechanical ventilation in days commencing at randomisation and discontinuing at first successful unassisted breathing or death.

Successful unassisted breathing is defined as breathing unassisted at 48 hours with no inspiratory support or extracorporeal lung support. Duration of assisted breathing includes time receiving extracorporeal lung support, invasive mechanical ventilation and non-invasive ventilation delivering volume or pressure support ventilation; **excludes** high-flow oxygen therapy and continuous positive airway pressure.

This definition was agreed through an international consensus process, involving clinician, researcher, patient and family representatives, and industry [17]. This primary outcome was chosen with Public and Patient Involvement (PPI) input.

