1 TRIAL SUMMARY

Table 1. Trial summary

Master protocol title	CoReCCT - Confederation of Respiratory Critical Care Trials
Domain protocol title	Neurally Adjusted Ventilatory Assist (NAVA) Technology (diaphragm monitor and NAVA mode) vs conventional invasive mechanical ventilation (IMV) for patients at risk of difficult or prolonged weaning from IMV: The UK NAVA Trial
Short title/acronym	UK NAVA
Clinical phase	Phase 3 effectiveness & cost-effectiveness
Purpose of research	To investigate, using a multi-centre, parallel group, pragmatic, randomised controlled trial design, the clinical and cost effectiveness of Neurally Adjusted Ventilatory Assist (NAVA) compared to conventional IMV in adult patients with risk factors for difficult or prolonged weaning from IMV treatment
Trial design	Parallel group randomised controlled trial with internal pilot and cost effectiveness analysis
Participants	Adult ICU patients who are at risk of difficult or prolonged weaning from IMV
Planned sample size	900
Treatment duration	≤28 days
Follow-up duration	6 months following randomisation
Planned trial period	May 1 st 2024 to 31 st September 2028
Inclusion criteria	
 1. Age 18 years or over 2. Receiving invasive mechanical ventilation 3. Expected to stay on IMV for ≥48hrs 4. Any clinical risk factor for difficult or prolonged weaning from IMV
Intervention	NAVA technology uses a specialised nasogastric/orogastric tube (NAVA catheter) to obtain the electrical activity of the diaphragm (EDi) muscle, which is a reliable index of the patient's respiratory drive. Once the NAVA catheter is placed, the EDi is always visible to clinicians, allowing optimisation of ventilator settings in any mode. When the NAVA mode is active, the ventilator triggers, cycles and adjusts support in synchrony and proportion to the EDi.
Control	Conventional invasive ventilator modes (no NAVA Technology)
Primary outcome	Duration of mechanical ventilation (time from randomisation to first successful unassisted breathing or death)
Secondary outcomes	
 1. All-cause mortality at hospital discharge, 2 months and 6 months after randomisation 2. Time to first extubation

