2.3 PILOT FEASIBILITY TRIAL AND SURVEYS

To test the feasibility of our trial protocol, we conducted a randomised pilot feasibility trial ($n=78$) [12], a detailed staff survey ($n=301$) [13] and a national clinician survey (unpublished).

Pilot trial results summary

The NAVA mode was initiated successfully in 31/34 (91%) intervention arm patients with median adherence (proportion of eligible weaning time spent in the NAVA mode) of 83.1% (64.0 to 97.1%). Diaphragm monitoring was active in all but one intervention arm patient. In secondary outcomes, the trial found more days free of ventilation at day 28 (median difference (MD) 3.0 days, 95% CI 0.0–11.0; $p = 0.04$), fewer in-hospital deaths (relative risk 0.5, 95% CI 0.2–0.9; $p = 0.032$) and a non-significant difference in mechanical ventilation duration (MD 3.0 days, 95% CI 0.4 to 8.6; $p = 0.13$).

Staff survey results summary

The survey was conducted shortly before the end of recruitment to the pilot trial, and explored attitudes, beliefs and barriers to NAVA Technology use and research. Of the 466 questionnaires distributed, 301 (64.6%) were returned including responses from 236 nurses (78.4%), 53 doctors (17.6%) and 12 physiotherapists (4.0%). In summary the survey found broad support for NAVA use, belief in safety and clinically efficacy, and support and equipoise for research. It also found a perception complexity compared with PSV, low confidence among users and a need for improved training. These findings have informed training materials, study documents and practical measures to improve the intervention and methods of our proposed study.

National survey results summary

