3 TRIAL DESIGN

3.1 TRIAL SUMMARY AND FLOW DIAGRAM

We will conduct a multi-centre, randomised, allocation concealed, controlled, open label, pragmatic, parallel group clinical and cost effectiveness trial with an internal pilot. The internal pilot will run for 6 months in 10 sites (with staggered starts to facilitate site initiation visits and site support). The internal pilot will use identical processes as the main trial and will assess site set-up, screening, participant recruitment, protocol adherence, and cross over rates. Progression criteria are outlined below. All participants included in the internal pilot will be included in the final analyses. The trial will be reported in line with the CONSORT (*Consolidated Standards of Reporting Trials*) statement.³⁸

Once the pilot has been completed sites will be opened as soon as possible in a phased manner ideally over a 10-month period. It is expected around 30 more sites will be opened and recruitment is anticipated to continue for a total of 37 months.

PICO summary

[figure not shown]
Population: Critically ill adults receiving IMV and at risk of difficult or prolonged weaning

Intervention: NAVA Technology (NAVA monitoring and NAVA mode)

Comparator: Conventional invasive ventilator modes (no NAVA Technology)

Outcome: Duration of invasive mechanical ventilation from randomisation (primary clinical effectiveness), plus cost-utility at 6-months

Figure 1. Trial flow diagram

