8.2 STATISTICAL ANALYSIS

The trial results will be reported in accordance with the Consolidated Standards of Reporting Trials (CONSORT). Primary analysis will be intention-to-treat. For our primary analysis, a cox-proportional hazard model will be used to estimate hazard ratio with 95% confidence interval (CI). If the proportional hazard assumption is not valid, we will run a sensitivity analysis by fitting a mixed effects partially proportional hazards regression model with censoring for deaths and loss to follow-up. Although death in ICU may be considered a competing event, censoring for deaths allows us to estimate the instantaneous risk of experiencing a successful extubation event at time t given that the patient is still alive at time t (known as “cause-specific hazard” of extubation for patients who have not yet died). Sites will be included in the model as a random effect, and treatment arm as a fixed effect. For secondary outcomes including quality-of-life measures which are continuous, mixed-effect linear regression models will be used to estimate the treatment effect with 95% CI. For secondary outcomes which are binary, mixed-effect logistic regression models will be used to estimate the treatment effect with 95% CI. We will explore different approaches that allow incorporation of multiple relevant outcomes including death into a single overall measure (e.g., win ratio [18]). A detailed statistical analysis plan will be agreed with the data monitoring committee.

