8.4 FUTILITY ANALYSES

The methods for futility analyses and determining futility boundaries which account for censored observations are very limited in the literature. Assuming there is no censoring (and for every patient, an event will be observed), we can use normal approximation methods for the log hazard ratio. This assumption is reasonable in the context of this study. In consultation with the DMC, we aim to plan for a futility analysis halfway through our trial (at 50% sample size). We will use the conventional conditional power boundaries at this interim point, where we will declare for futility if the conditional power is <15%. Assuming our hazard ratio is 1.25 (as per the sample size), this interim analysis (and boundaries) does not impact on the overall study power of 90%. This futility rule will be used as a guidance criterion by the DMC. The decision to stop will be based largely on clinical judgement of all the outcomes, as well as parameters that drive operational futility (recruitment).

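### Death has incompatible roles in the primary analysis: the sample size and futility rule need it to be an event, section 8.2 censors it, and the primary Cox model's event is never stated

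*Protocol*

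**What the plan says.** **End of the outcome.** Section 3.4.1 states: "Our primary outcome is duration of mechanical ventilation in days commencing at randomisation and discontinuing at first successful unassisted breathing or death". Table 1 agrees: "time from randomisation to first successful unassisted breathing or death". Neither gives a patient who dies a different value or status from one who is liberated. The objective in 3.4.1 is to "determine the effectiveness of NAVA technology for reducing the duration of mechanical ventilation", so a shorter time is the favourable direction.

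**Primary model.** Section 8.2 names a Cox model without saying what its event is or who is censored. Death is first mentioned in the next sentence, on a sensitivity analysis for failed proportional hazards: a "mixed effects partially proportional hazards regression model with censoring for deaths and loss to follow-up". The text then defends censoring because it estimates "the instantaneous risk of experiencing a successful extubation event at time t given that the patient is still alive" at that time, which it calls a cause-specific hazard.

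**Futility.** Section 8.4 works from "Assuming there is no censoring (and for every patient, an event will be observed") and calls this reasonable for the study. It also gives the design hazard ratio as 1.25.

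**Sample size.** Section 8.1 plans 900 patients for 90% power at the 5% level with 5% loss to follow-up, a control median of 10 days and a 2-day reduction. It makes no allowance for deaths.

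**Name of the event.** Section 3.4.1 uses successful unassisted breathing and counts non-invasive volume or pressure support as assisted time. Sections 3.11 and 8.2 speak of successful extubation. The PICO summary in 3.1 has "Duration of invasive mechanical ventilation from randomisation (primary clinical effectiveness").

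**The concern.** A patient who dies on the ventilator has an event under the premise of 8.4 and is censored under the reasoning of 8.2. These are two different estimands, and the protocol uses both. Leaving detail to the SAP does not settle this, because the protocol already fixes the point in conflicting ways.

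If death is an event, it ends the clock just as liberation does and an earlier death scores as a shorter duration. Excess deaths on NAVA would then push the hazard ratio towards benefit, and fewer deaths would push it towards harm. A difference in mortality is not far-fetched: section 2.3 reports from the feasibility trial "fewer in-hospital deaths (relative risk 0.5", 95% CI 0.2-0.9).

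If death is censored, the event count behind the 900 is not reached.

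Section 8.2 also ties the handling of death to a check of proportional hazards. Whether hazards are proportional says nothing about whether death should count as an event.

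The shifting event name adds to this. A patient extubated onto pressure-support non-invasive ventilation has been extubated but does not yet meet the 3.4.1 definition. Time to first extubation is a separate secondary outcome, so the two terms are not interchangeable.

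**Working it through.** **Inputs from the protocol.** N = 900, allocated 1:1 (3.8); 90% power, 5% level, 5% loss to follow-up, control median 10 days, reduction 2 days (8.1); hazard ratio 1.25 (8.4). The protocol does not state sidedness; two-sided is taken because one-sided gives only 725 or 731 patients.

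**Assumptions.** Hazards are constant. The share *d* of control exits from ventilation that are deaths is not given; 20% and 30% are used.

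**Step 1: reproduce the 900.** The hazard ratio is 10/8 = 1.25.
- Schoenfeld: events = 4(1.960 + 1.282)² / (ln 1.25)² = 845; 845/0.95 = 890.
- Freedman: events = (1.960 + 1.282)² × (2.25/0.25)² = 852; 852/0.95 = 897.

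Both match 900. Followed patients number 900 × 0.95 = 855, so 845-852 events means practically one event per followed patient. That requires deaths to count as events, or nobody to die before liberation. The 5% loss allowance cannot absorb deaths, because 8.1 derives it from loss to follow-up in earlier trials.

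**Step 2: if death is an event.** The composite hazard ratio is (1 − *d*) × HR for liberation + *d* × HR for death. The chance of significance in the direction of the effect is Φ(√(855/4) × |ln HR| − 1.96), with √(855/4) = 14.62.

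| Liberation HR | Death HR | Composite HR, d = 20% / 30% | Chance of significance |
|---|---|---|---|
| 1.00 | 1.5 | 1.10 / 1.15 | 29% / 53%, apparent benefit |
| 1.00 | 0.5 | 0.90 / 0.85 | 34% / 66%, apparent harm |
| 1.25 | 1.0 | 1.20 / 1.175 | 76% / 65%, benefit |
| 1.25 | 0.5 | 1.10 / 1.025 | 29% / 5.5%, benefit |

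Example, first row with *d* = 30%: 0.7 × 1.00 + 0.3 × 1.5 = 1.15; 14.62 × ln 1.15 = 2.04; Φ(2.04 − 1.96) = 53%. The NAVA median would read 10/1.15 = 8.7 days with no effect on liberation.

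The third row shows that counting deaths does not secure 90% power either, if 1.25 is the effect on liberation and the death hazard is unchanged.

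**Step 3: if deaths are censored.** Take the same death share in both arms and a liberation hazard ratio of 1.25. Power is Φ(√(events/4) × ln 1.25 − 1.96).

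| Death share | Liberation events among 855 | Power at 900 | N for 90% power (Schoenfeld to Freedman) |
|---|---|---|---|
| 0% | 855 | 90% | 890-897 |
| 20% | 684 | 83% | 1,112-1,122 |
| 30% | 598.5 | 78% | 1,271-1,282 |

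The last column is the required events divided by (1 − *d*) × 0.95; for 20%, 845/(0.80 × 0.95) = 1,112.

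**The case against.** A reader might infer that the primary Cox model is specified to treat death as a favourable event. The protocol does not say so. Section 8.2 leaves the primary event undefined. Table 1 and 3.4.1 say when the duration ends, not what status the patient then has, and a cause-specific analysis also ends follow-up at death. The argument for censoring in 8.2 is worded generally and is followed by model terms that could apply to every model, so it may be meant to cover the primary analysis. This part of the objection stands: death as an event is one reading, and it is the reading that 8.1 and 8.4 rely on.

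It can also be said that 8.4 makes a working assumption for a non-binding guidance rule. That is true, and 8.4 does not define the primary event. But the assumption is incompatible with censoring deaths, and 8.1 depends on the same event count. The generous reading of 8.2 therefore moves the conflict to the power and does not remove it.

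The scenarios in Step 2 are hypothetical. A reader might take the feasibility trial's relative risk of 0.5 as evidence for the death hazard ratios used. It is not: it concerns in-hospital death in 78 patients, not death before liberation. Nothing in the protocol suggests excess deaths on NAVA.

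All-cause mortality is a secondary outcome and a win ratio will be explored, so a mortality difference would be seen. Neither corrects the primary hazard ratio. The consensus origin of the outcome definition does not settle event against censoring in a Cox model. The varying event names alone would be a minor wording point.

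**Conclusion.** The inconsistency is real and should be resolved before the analysis is fixed. The basis of the 900 and the futility premise both need an event from practically every followed patient, while 8.2 censors deaths and argues for a cause-specific hazard.

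Each way of resolving it has a price. With death as an event, the primary hazard ratio mixes survival with weaning: under no effect on liberation, a death hazard ratio of 1.5 produces a significant apparent benefit in 29-53% of trials. With deaths censored, power at 900 is about 83% at 20% deaths and 78% at 30%.

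These figures rest on constant hazards, 855 evaluable patients and an assumed death share of 20-30%; the power figures also assume equal death shares by arm. The protocol supplies no death rate, so the sizes are illustrative. The contradiction itself depends on none of these assumptions.

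**What to change.** 1. State one primary event in Table 1, 3.1, 3.4.1, 3.11, 8.1, 8.2 and 8.4: first successful unassisted breathing as defined in 3.4.1, with death before it not an event.
2. In 8.2, make the cause-specific Cox model that the section already defends the unconditional primary analysis. Remove the link between censoring of deaths and failure of proportional hazards.
3. Always report beside it the cumulative incidence of liberation with death as a competing event, and the hazard of death by arm. The cause-specific hazard ratio alone does not show whether more patients were liberated or fewer died.
4. In 8.1, state an expected share of deaths before liberation with its source, and restate the power of 900 patients for that share. If 90% is to be kept, the Step 3 table shows the numbers needed.
5. In 8.4, replace the no-censoring premise and express the halfway point in liberation events. With 20% deaths, half of the sample gives about 684/2 = 342 events, against 855/2 = 428 under the present premise.

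The cost is wording in seven places and one additional analysis on data that Table 4 already collects. The downside is a less favourable stated power, unless the sample size is raised.

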3.4.2 SECONDARY OBJECTIVES AND OUTCOMES

Our secondary objectives are to determine the effect of NAVA technology compared to conventional IMV on the following:

- All-cause mortality (2 months and 6 months from randomisation)
- Time to first extubation
- Reintubation
- Use of non-invasive ventilation following extubation
- ICU and hospital length of stay
- Serious adverse events up to hospital discharge
- HRQoL at 2 months and 6 months from randomisation
- Acute health care use at 6 months following randomisation
- Within-trial cost-utility analysis from an NHS hospital care perspective (see below)

- Safety endpoints (see also section 'Serious adverse events up to hospital discharge')
- Pre-specified complications including
 - Naso-gastric tube entering brain
 - Naso-gastric tube positioned in lungs (unrecognised/not corrected)
 - Traumatic nasogastric catheter insertion (oesophageal perforation)
 - Traumatic nasogastric catheter insertion (nasal/pharyngeal bleeding)
 - Aspiration of stomach contents
 - Pneumothorax
 - Unplanned removal of ETT or Tracheostomy
 - Unplanned removal of naso-gastric tube
 - Unplanned removal of any other invasive/indwelling device
 - Any pressure injury caused by naso-gastric catheter
 - MRI scan performed with NAVA naso-gastric catheter in situ
 - Reportable safety events that fall outside of those reported as trial outcomes

3.4.3 COST-EFFECTIVENESS OBJECTIVE

To estimate the cost-effectiveness of NAVA compared to conventional IMV.

3.5 TRIAL PARTICIPANTS

Patients who meet all the following inclusion criteria and none of the exclusion criteria are eligible to participate in the trial.

3.5.1 INCLUSION CRITERIA

- Age 18 years or over
- Receiving IMV
- Expected to stay on IMV for ≥ 48 hrs
- Any clinical risk factor for difficult or prolonged weaning from invasive ventilation*

3.5.2 EXCLUSION CRITERIA

- Death or treatment withdrawal imminent within 48 hours
- 1. Contraindication to NG or orogastric tube insertion, such as upper airway or oesophageal trauma, bleeding or risk of bleeding due to recent surgery, oesophageal varices or portal hypertension, and skull base fracture
- An active cardiac pacemaker or phrenic nerve injury, due to their impact on the EDi signal
- Severe central neurologic disorder (e.g., traumatic brain injury, haemorrhage, stroke, tumour) causing elevated intracranial pressure, or impaired control of breathing, or requiring specific ventilator adjustments (i.e., to attain specific CO₂ target) or requiring neurosurgical intervention
- Known or suspected severe or progressive neuromuscular disorder likely to result in prolonged or chronic ventilator dependence (e.g., Motor Neuron Disease, Duchenne Muscular Dystrophy, Amyotrophic Lateral Sclerosis, Multiple Sclerosis, high spinal cord injury, Kyphoscoliosis, or other restrictive disorder).
- Severe, end-stage, irreversible respiratory or cardiac disease likely to result in chronic ventilator dependence (e.g. interstitial lung disease, pulmonary fibrosis, cardiomyopathy, valvulopathy)

- Continuous therapeutic neuromuscular paralysis
- Home ventilation prior to ICU admission, excluding nocturnal CPAP
- Previous participation in the UK NAVA trial

3.6 SCREENING

All ventilated ICU patients will be screened daily for eligibility by the ICU research nurses or medical staff. Each site will maintain a screening log which will include data on the numbers of patients meeting eligibility criteria but not entered into the trial, those that consent but are then not enrolled, numbers not meeting inclusion criteria, and reasons for non-enrolment. A fully anonymised patient level minimal dataset (including age, sex, ethnicity, and reasons for non-enrolment) will be recorded to establish an unbiased study population and for reporting according to the CONSORT statement [27,28].

3.7 CONSENT

It is the responsibility of each site Principal Investigator (PI) (or designee) to ensure that written informed consent is obtained for each participant prior to entry into the trial. Consent may be obtained by the PI, or an appropriately trained member of the site team provided they are GCP trained, suitably qualified and experienced and have been delegated this duty by the PI on the delegation log.

Eligible patients will be unable to give informed consent because of sedation and IMV. In most cases (in England, Wales and Northern Ireland), it is expected that advice will be sought from an appropriate consultee prior to randomisation. In some circumstances, where there is a limited window of opportunity to insert an NAVA catheter, it may not be possible to seek prior assent from an appropriate consultee prior to randomisation. Opportunities for NAVA catheter insertion commonly occur in the early acute phase of illness, when patients are sedated. This reduces patient discomfort due to the existing sedation and analgesia, and reduces the risks involved in nasogastric/orogastric tube removal and replacement. For these reasons, we will seek approval from a research ethics committee to use a deferred consent model. For sites in Scotland, it is expected that advice will be sought from an appropriate Welfare Guardian/Nearest Relative. In cases where no Welfare Guardian/Nearest Relative is available it will not be legally possible to enrol the participant (specific to the Adults with Incapacity Act Scotland for non-CTIMP trials).

Once a participant who initially lacks capacity, regains capacity, they will be informed about the trial and invited to consent to continue in the trial. There is no requirement to reaffirm consent in Scotland.

Further details on the consent process are detailed in section 4.2.3 of the CoReCCT master protocol.

